9.3 Baseline Evaluation

As part of the screening process, subjects will undergo a standard physical exam including a physical examination of the target limb and medical history (review of symptoms, pre-existing conditions, and medications). The baseline review will also capture information on the target AVF (location, age, and previous re-interventions). A Numeric Rating Scale (NRS) will be collected to assess pain at the access site. Although not required by the protocol, any laboratory tests/results performed by the treating physician as part of standard care to evaluate the patient will be collected.

9.4 Index Percutaneous Intervention Procedure – Prior to Randomization

- During and after the procedure, the appropriate anti-coagulants, anti-platelet agents and vasodilators should be administered to the patient according to the institutional practice.
- A pre-enrollment fistulogram is performed to assess whether the subject meets the anatomic eligibility criteria for the target lesion per section 8.
- Cross the lesion with a guidewire.

9.5 Subject Enrollment and Randomization

A subject will be enrolled in the study after he/she has signed the informed consent, it has been determined that he/she meets all the inclusion criteria and none of the exclusion criteria, and the guidewire has successfully crossed the lesion selected for treatment. If the lesion cannot be crossed, it will be classed as a screen failure. All information collected up until the point of screen failure, including the informed consent form, demographics, and procedure information, will be stored in a Screening Binder.

Once the patient is enrolled, they will be randomized in a 1:1 fashion into the TEST Arm or CONTROL Arm by using sealed envelopes. Randomization will follow a permuted block design and be stratified by site. After confirming the lesion can be crossed with the guidewire, the

site will open the envelope that is next in sequence and assign the corresponding Subject ID number. Envelopes containing the randomization assignment and Subject ID number (beginning with 001) will be stored in the Subject Binder.

9.6 Index Percutaneous Intervention Procedure – After Randomization

9.6.1 TEST Arm: FLEX Vessel Prep™ System and PTA

- FLEX Vessel Prep is placed over an 0.14" or 0.18" guidewire and advanced distal to the lesion to be treated. Following procedural guidelines in the Instructions for Use, the FLEX Vessel Prep System is used to create circumferential, continuous micro-incisions along the length of the stenosis by performing a retrograde pullback through the lesion.
- Post use of the FLEX Vessel Prep, a fistulogram of the AV access circuit is obtained.
- Standard Balloon angioplasty is performed with an uncoated PTA balloon sized to meet the reference vessel diameter, according to its corresponding instructions for use. Once advanced to the lesion, the balloon should be inflated according to the site's standard of care.
 - Note 1: During balloon inflation, **opening/effacement pressure** (defined as minimum inflation pressure required to efface target lesion noting parallel balloon walls) and **maximum pressure** (defined as highest pressure required during index procedure to treat target lesion) will be assessed.
 - Note 2: Administer the NRS to the subject to identify the highest level of pain experienced during the procedure.
- A fistulogram is obtained of the final PTA result.
- Record procedural data on the CRFs.

9.6.2 CONTROL Arm: PTA

- Optional: A standard uncoated PTA balloon is sized to meet the reference vessel diameter, according to its corresponding instructions for use. The balloon is placed over an appropriate guidewire and advanced to the lesion. The balloon is inflated to pre-dilate the lesion according to its instructions for use and the site's standard of care.
 - Note 1: During balloon inflation, **opening/effacement pressure** (defined as minimum inflation pressure required to efface target

lesion noting parallel balloon walls) and **maximum pressure** (defined as highest pressure required during index procedure to treat target lesion) will be assessed.

- Post pre-dilation, a fistulogram of the AV access circuit is obtained.
- Standard Balloon angioplasty is performed with an uncoated PTA balloon sized to meet the reference vessel diameter, according to its corresponding instructions for use. Once advanced to the lesion, the balloon should be inflated according to the site's standard of care.
 - Note 1: During balloon inflation, **opening/effacement pressure** (defined as minimum inflation pressure required to efface target lesion noting parallel balloon walls) and **maximum pressure** (defined as highest pressure required during index procedure to treat target lesion) will be assessed.
 - Note 2: Administer the NRS to the subject to identify the highest level of pain experienced during the procedure.
- A fistulogram is obtained of the final PTA result.
- Record procedural data on the CRFs.

9.6.3 Stent Placement

Placement of a stent or stent graft should be avoided unless required for subject safety.

Stent placement should be performed only after repeated and prolonged balloon inflations result in either of the following conditions:

- Residual stenosis of $\geq 50\%$ (by visual estimate)
- Major (\geq Grade D) flow-limiting dissection

All subjects who undergo a stenting are required to be followed per the protocol-required follow-up schedule.

9.6.4 Discharge

All subjects will be evaluated for serious adverse events (SAEs) and complications prior to discharge.

9.7 Follow-up Requirements

The subject will be followed after 30 days, 3 months and 6 months post procedure.

The following assessments will be performed during these follow-ups:

- Evaluation for SAE's
- Patency of Access Site
- Access Circuit Reintervention Information

If the access site used in the study is abandoned, the subject should be withdrawn from the study.

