14.7	SUSPENSION OR EARLY TERMINATION	26
15	REFERENCES	26

2 Definitions

Term	Definition
Access Circuit	The area from the AV access fistula arterial anastomosis to the axillosubclavian junction.
Access Thrombosis	A total occlusion within the AV access circuit due to thrombus formation which is rapidly evolving as confirmed by sudden onset of symptoms and documented by duplex ultrasound and/or angiography.
Arteriovenous "Dialysis" Fistulae (AVF)	The joining of an artery and vein for the purpose of hemodialysis access.
Clinical Success	Resumption of successful dialysis for at least one session after index procedure.
De Novo Lesion	A lesion that has not been previously treated.
Device Success	Successful delivery, treatment, and retrieval of the FLEX Vessel Prep System or the control device at index procedure.
Dissection Types A-F	
Intimal disruption of the vessel wall with or without medial or adventitial contrast staining, classified as per the NHLBI (National Heart, Lung, and Blood Institute) criteria as follows:
 
A) Luminal Haziness: Minor radiolucent areas in the lumen without impairment of flow or persistent dye staining after contrast runoff.
 
B) Linear Dissection: Luminal flap that is radiolucent and that runs parallel to the vessel wall with contrast injection but without impairment of flow or persistent dye staining after contrast runoff.
 
C) Extraluminal Contrast (i.e., "cap dissection"): Contrast appears outside of the vessel lumen as an "extraluminal cap." The staining appears even after contrast clears the lumen.
 
D) Spiral Dissection: Spiral radiolucent luminal filling defects; often persistent staining after contrast clears from the vessel.
 
E) Dissection with Reduced Flow: New and persistent filling defects in the vessel lumen
 
F) Dissection with Total Occlusion: Lesions that progress to

Term	Definition
	impaired flow or total occlusion
Embolism	The obstruction of a blood vessel by a foreign substance or a blood clot that travels through the bloodstream, lodging in a blood vessel or plugging the vessel.
Enrollment	The time the guidewire has successfully crossed the lesion to be treated.
Optimal PTA	Repeated and prolonged balloon inflations aimed to achieve <50% residual stenosis (visual estimate) without stenting.

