Target Lesion Re-intervention (TLR)	
Any repeat invasive procedure, including angioplasty, stenting or thrombolysis, performed to open or increase the lumen diameter within the previously treated lesion.
 
Clinically-Driven Target Lesion Re-intervention (CD-TLR): Any re-intervention involving the target lesion in which:
 
 • The subject has a $\geq 50\%$ diameter stenosis in the presence of clinical or physiologic abnormalities that indicate dialysis access dysfunction OR • $\geq 70\%$ stenosis with or without the presence of clinical or physiologic abnormalities indicating dialysis access dysfunction. 
Non-Clinically-Driven Target Lesion Re-intervention: any re-intervention involving the target lesion which does not meet the criteria for CD-TLR.

* Defined by National Kidney Foundation KDOQI Guidelines

3 Protocol Summary

Title	FLEX Vessel Prep prior to PTA for the Treatment of Obstructive Lesions in the Native Arteriovenous Dialysis Fistulae (AVF)
Clinical Study Type	Post Market Outcomes Research Study
Study Device	FLEX Vessel Prep System
Sponsor	VentureMed Group, Inc. [name]
Study Purpose	To evaluate and compare the serious adverse event rate at 30 days and primary patency at 6 months when using FLEX Vessel Prep System prior to PTA vs. PTA alone for treatment of obstructive lesion of native arteriovenous fistulae in the upper extremity.
Primary Efficacy Endpoint	Target Lesion Primary Patency Rate through 6 Months Defined as freedom from clinically driven target lesion re-intervention (CD-TLR) or access circuit thrombosis measured through 6 months post-procedure.
Primary Safety Endpoint	Serious Adverse Event Rate within 30 Days Defined as the Serious Adverse Event (SAE) rate involving the AV access circuit through 30 days post-procedure.

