In the United States there are approximately 468, 000 patients with end stage renal disease (ESRD) who require routine hemodialysis (HD) as their renal replacement therapy. Among prevalent patients as of December 2018, more than four out of every five patients receiving hemodialysis were using an AV fistula or graft (82.4%; 65.7% fistula and 16.7% graft¹).

The natural history of a hemodialysis access is the persistent development of neointimal hyperplastic stenoses. In fistulas, the most common location of stenoses depends upon the type of fistula. Radial artery-cephalic vein fistulas often develop juxta-anastomotic stenoses, brachial artery to cephalic vein fistulas develop cephalic arch stenoses, often at the site of a hypertrophied valve ring and brachial artery to transposed basilic vein have a predilection to develop stenosis at the swing point of the vein.²

These stenoses cause a reduction in blood flow through the access and thereby decrease the ability to deliver effective hemodialysis treatment. If left untreated, these aggressive lesions will eventually cause the access to thrombose.

Percutaneous transluminal balloon angioplasty (PTA) is the primary technique for treatment of neointimal stenoses associated with prosthetic hemodialysis grafts and native fistulas. It remains the standard treatment to which other percutaneous techniques are compared.

Limitations of PTA include:

- Post angioplasty elastic recoil. After being dilated, elastic elements in the vessel wall cause immediate decrease in lumen diameter.
- Inability to fully dilate a lesion: Dense intimal hyperplasia can be resistant to expansion. Ultra-High-pressure balloons are needed which increase patient discomfort and the risk of vessel rupture.
- Recurrent stenosis.³

Although an angioplasty procedure can provide an excellent immediate result, the long-term patency rates are less than satisfactory with patients requiring an average 1.9 interventions per year.⁴ Clinical studies describing the use of angioplasty to treat hemodialysis fistula-related stenoses have reported six-month patency rates of 25 – 78%.⁵ Angioplasty failures may be due to acute elastic recoil, vascular rupture during balloon inflation or rapid re-growth of the neointimal stenosis. Subsequent dysfunction of the dialysis circuit is a significant cause of morbidity and mortality in patients undergoing HD which results in repeated interventions and can eventually lead to loss of vascular access.

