5.2 Endpoints

5.2.1 Primary Endpoints

Primary endpoints for the study are as follows:

- Primary Efficacy Endpoint: Target Lesion Primary Patency Rate through 6 Months

Defined as freedom from clinically driven target lesion re-intervention (CD-TLR) or access circuit thrombosis measured through 6 months post-procedure.

- Primary Safety Endpoint: Serious Adverse Event Rate within 30 Days

Defined as the Serious Adverse Event (SAE) rate involving the AV access circuit through 30 days post-procedure.

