5.2.2 Secondary Endpoints

Secondary endpoints assessed through 6-months (unless noted otherwise) for the study are as follows:

- Secondary Safety Endpoint: Serious Adverse Event Rate within 3 and 6 Months

Defined as the Serious Adverse Event (SAE) rate involving the AV access circuit through 3 months and 6 months post-procedure.

- Access Circuit Primary Patency through 3 Months and 6 Months Post-Procedure
Defined as freedom from re-intervention in the access circuit or access circuit thrombosis through 3 months and 6 months post-procedure.
- Target Lesion Primary Patency through 3 Months and 6 Months Post- Procedure
Defined as freedom from CD-TLR or access thrombosis occurring in the target lesion through 3 months and 6 months post-procedure.
- Cumulative Target Lesion Reinterventions Measured through 3 Months and 6 Months Post-Procedure
Defined as proportion of subjects with TLR through 3 months and 6 months post-procedure.
- Number of Interventions Required to Maintain Target Lesion Patency through 3 Months and 6 Months Post-Procedure
Defined as number of TLR through 3 months and 6 months post-procedure.
- Number of Interventions Required to Maintain Access Circuit Patency through 3 Months and 6 Months Post-Procedure
Defined as number of reinterventions in the target lesion and/or access circuit through 3 months and 6 months post-procedure.
- Cumulative Access Circuit Thromboses Measured through 3 Months and 6 months Post-procedure.
Defined as proportion of subjects with access circuit thrombosis through 3 months and 6 months post-procedure.
- **Device Success:** Defined as successful delivery, treatment, and retrieval of the FLEX Vessel Prep device at index procedure.
- **Procedural Success:** Defined as maintenance of patency ($\leq 30\%$ residual stenosis) in the absence of peri-procedural Serious Adverse Event (SAE).
- **Clinical Success:** Defined as resumption of successful dialysis for at least one session after index procedure.
- **Balloon opening pressure** Defined as minimum inflation pressure required to efface target lesion noting parallel balloon walls.
- **Maximum balloon pressure** of angioplasty balloon(s) required during the interventional procedure to treat target lesion.
- **Patient Reported Pain** During the interventional procedure reported via Numerical Rating Scale (NRS).

6 Study Design

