This is a prospective, multi- center, randomized (1:1) clinical study evaluating the FLEX Vessel Prep System followed with PTA (TEST arm) vs PTA alone (CONTROL arm) for the treatment of *de novo* or non-stented restenotic obstructive lesions up to 100 mm in length located in the arteriovenous dialysis fistulae in an upper extremity. Enrollment will continue until complete data sets are collected for up to 75 subjects from up to 7 sites in the US.

Once enrolled, subjects will remain in the study through completion of the required follow-up duration unless the subject withdraws consent, the subject expires, the investigator withdraws the subject, or VentureMed terminates the study for any reason. The enrollment phase is expected to take 3 months. The follow-up duration for each subject is up to 6 months. The total expected duration of the study is approximately 9 months.

7 Product Description

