10.2 Potential Benefits

There are no guaranteed benefits from participation in the study. It is possible that treatment with the FLEX Vessel Prep System prior to use of PTA may improve and maintain blood flow through the treated AVF, resulting in the need for fewer treatments. This may allow for continued/resumption of AV access for the purpose of hemodialysis. Additionally, it is possible that lower balloon inflation pressures following FLEX Vessel Prep use will result in fewer complications and potentially less pain experienced during the procedure. Information gained from the conduct of this study may be of benefit to other persons with the same medical condition.

11 Serious Adverse Event Assessments

The Investigator is required to assess and document in the medical record all Serious Adverse Events (SAEs) observed in subjects from the time of enrollment until the event resolves or the subject exits the study. In cases in which SAEs are unresolved at the time of study exit, this will be documented on the CRF.

The Investigator is responsible for reporting SAEs to VentureMed as soon as possible, but no later than 10 working days after the Principal Investigator is first aware of the event, by completing the Adverse Event CRF. The Principal Investigator is responsible for reporting the SAE to the IRB as applicable.

12 Statistical Design and Methods

This is a prospective, multicenter, randomized (1:1) study of FLEX Vessel Prep prior to PTA vs PTA alone for the treatment of de novo and non-stented restenotic lesions in the AVF. The study will enroll at up to seven centers in the US.

Comparison of binomial proportions will be performed using Fisher's exact test. Time-to-event analyses using the Kaplan-Meier method may be conducted to supplement the primary analysis of proportions. Comparisons of continuous variables will be performed using a two-sample t-test or Wilcoxon rank-sum test.

For the primary efficacy endpoint and other 6-month endpoints that compare the proportion of subjects between arms, the numerator is the number of subjects with an event within 6 months and the denominator is the number of subjects with an event or who were followed for at least 150 days.

For the primary safety endpoint and other 30-day endpoints that compare the proportion of subjects between arms, the numerator is the number of subjects with an event within 30 days and the denominator is the number of subjects with an event or who were followed for at least 23 days.

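### Abandonment of the target AVF is not a patency event, so failure-type abandonments leave the 6-month patency proportion or count as patent, and the supplied text gives no sensitivity analysis

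*Combined protocol and SAP*

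**What the plan says.** - **Withdrawal.** Section 9.7: "If the access site used in the study is abandoned, the subject should be withdrawn from the study". Section 9.9.3 names abandonment among the exits whose reason must be recorded on the Exit Form, and Table 1 has a column for it.
- **Primary efficacy endpoint.** Section 5.2.1: "Defined as freedom from clinically driven target lesion re-intervention (CD-TLR) or access circuit thrombosis measured through 6 months post-procedure".
- **Access circuit primary patency (secondary).** Section 5.2.2: "Defined as freedom from re-intervention in the access circuit or access circuit thrombosis through 3 months and 6 months post-procedure".
- **Component events.** In Section 2 a target lesion re-intervention is a repeat invasive procedure "performed to open or increase the lumen diameter within the previously treated lesion". Access thrombosis is a total occlusion from thrombus that is "rapidly evolving as confirmed by sudden onset of symptoms and documented by duplex ultrasound and/or angiography".
- **6-month proportions.** Section 12 puts subjects with an event within 6 months in the numerator, and "the denominator is the number of subjects with an event or who were followed for at least 150 days".
- **Other analysis text.** The intent-to-treat analysis in Section 12 is limited to subjects with available follow-up data. Kaplan-Meier analysis is optional. Further methods are deferred to a Statistical Analysis Plan whose text is not in the supplied document.

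**The concern.** Giving up a fistula can be the end result of a failed access. The Section 4 background itself says that dysfunction of the circuit can lead to loss of vascular access. Yet abandonment alone is neither a procedure to open the lesion nor a documented thrombosis, so it triggers no endpoint event, and the withdrawal rule then ends follow-up. Whether the subject is analysed, and how, depends on the day of abandonment.

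Where abandonment reflects failure, a subject is dropped because of the outcome, or is counted as a success despite it. Section 12 says the study exists to estimate differences between groups. A reader given only the two proportions could not tell whether any abandonments lie behind them, in which arm, or whether they matter.

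**Working it through.** **1. What happens to an abandoned AVF** (Sections 5.2, 9.7 and 12 read together)

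| Situation | 6-month numerator (events) | 6-month denominator | Effect |
|---|---|---|---|
| Qualifying event, then abandonment | yes | yes | failure; not affected |
| No event, abandoned before day 150 | no | no | left out |
| No event, abandoned from day 150 up to 6 months | no | yes | counted as patent |
| No event, abandoned after 6 months | no | yes | event-free through 6 months; correct |

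The last row matters because Table 1 sets the 6-month visit at 180 ± 30 days, so follow-up can run to day 210.

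The intent-to-treat sentence does not restore the left-out subjects, because it covers only those with available follow-up data. Kaplan-Meier would normally censor them at withdrawal, which is informative censoring if abandonment reflects failure.

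**2. The plan's own precision figure**

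Section 12 gives ±25% at 60% v 80%. With 75 evaluable subjects (37.5 per arm):
- Wald: 1.96 × √[(0.6×0.4 + 0.8×0.2)/37.5] = 1.96 × 0.1033 = ±20.2%.
- With continuity correction: 20.2% + ½(1/37.5 + 1/37.5) = 20.2% + 2.7% = ±22.9%.
- Exact interval, 37 per arm: ±23.2%.

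The corrected formula reaches ±25% at about 64 evaluable subjects. The plan states neither the interval method nor the evaluable number, so this is not evidence of an error. I use ±25% only as a yardstick.

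**3. Size of the effect**

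No abandonment rate is given, so the counts below are assumptions. Inputs are 75 subjects at 1:1, taken as 37 control and 38 test, with patency near 60% and 80% (22/37 and 30/38), and everyone else evaluable.

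If a share *a* of an arm is failed-by-abandonment and excluded, the rule reports P/(1−a) instead of P. With a = 5%, 60% becomes 0.60/0.95 = 63.2% and 80% becomes 0.80/0.95 = 84.2%.

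*Reading 1: 75 randomized.* True status is 22/37 = 59.5% and 30/38 = 78.9%, a difference of 19.5 points. Excluding k failed-by-abandonment subjects gives 22/(37−k) and 30/(38−k):

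| k | Control | Test | Difference, k in each arm | Control only | Test only |
|---|---|---|---|---|---|
| 1 | 61.1% | 81.1% | 20.0 | 17.8 | 21.6 |
| 2 | 62.9% | 83.3% | 20.5 | 16.1 | 23.9 |
| 3 | 64.7% | 85.7% | 21.0 | 14.2 | 26.3 |
| 4 | 66.7% | 88.2% | 21.6 | 12.3 | 28.8 |

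*Reading 2: 75 evaluable.* Section 6 says "Enrollment will continue until complete data sets are collected for up to 75 subjects", so abandoned subjects may be additional to the 75. If 22/37 and 30/38 are the reported figures, adding back k failures gives 22/(37+k) and 30/(38+k). For k = 1 to 4, control falls from 57.9% to 53.7% and test from 76.9% to 71.4%. The difference becomes 19.0 to 17.8 (k in each arm), 17.5 to 12.0 (test only) or 21.1 to 25.3 (control only).

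Under either reading the first subject moves its arm by 1.6 to 2.1 points.

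*Abandoned from day 150 up to 6 months.* One failed access counted as patent gives 23/37 = 62.2% (up 2.7 points) or 31/38 = 81.6% (up 2.6 points).

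**4. Two-sided Fisher p, reading 1**

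No abandonment: 0.083. Two in each arm: 0.064. Two in control only: 0.195. Two in test only: 0.038. None of these splits is more likely than another.

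**The case against.** **The endpoint is as defined.** Under Section 5.2.1 an access abandoned on day 160 without re-intervention or thrombosis is event-free, so overstatement exists only if abandonment is regarded as loss of patency. This stands. It is why the definition should stay and the question be put in a sensitivity analysis.

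**The affected group is probably small.** Section 4 says of untreated stenoses that "these aggressive lesions will eventually cause the access to thrombose", and a documented thrombosis is already an event. Section 8.3 excludes anticipated conversion to peritoneal dialysis, infected access, planned surgical revision and steal requiring treatment. Section 8.2 requires a fistula with successful dialysis in 8 of 12 sessions. This stands and limits the weight of the point.

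**The same rule also pulls the other way.** It drops early exits without an event who might have stayed patent. Losing two such subjects per arm gives 20/35 = 57.1% and 28/36 = 77.8%, below 59.5% and 78.9%. So the net direction of the 150-day rule in an arm is not established; the statement here concerns failure-type abandonments only.

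**Stronger readings a reader might infer.**
- That both arms' patency is overstated. Only an arm with failure-type abandonments is affected.
- That the comparison is biased towards the test device. Nothing in the documents indicates which arm would have more abandonments.
- That the single p-value below 0.05 shows a threat to the conclusion. It comes from one assumed split, and Section 12 does not anticipate significance.
- That the sponsor has no rule for this. Section 12 defers detail to a Statistical Analysis Plan that is not supplied, so a rule there cannot be excluded.

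**Conclusion.** The concern holds in a limited form. As written, a target AVF abandoned with no prior event is left out of the 6-month patency proportions if this happens before day 150, and counts as patent from day 150 up to 6 months. Where abandonment reflects access failure, that arm's patency is overstated. The bias in the arm difference has no determined direction.

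The size is unknown. On the assumed counts, one subject is worth about 2 to 3 points in its arm, so one or two would be minor against ±25%. Three or four in one arm only would move the difference by about 5 to 9 points under reading 1. These figures rest on the planning rates, 75 subjects and no other loss to follow-up. This is a gap that is cheap to close, not a flaw that undermines the design.

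**What to change.** Leave the primary endpoint and the 150-day rule unchanged, and add to Section 12:

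> Sensitivity analysis: 6-month target lesion and access circuit primary patency will be re-estimated by arm, with the difference and 95% confidence interval, counting as loss of patency (a) abandonments of the target AVF within 6 months (the same cut-off day as for other 6-month events) whose recorded reason is access failure or dysfunction, and (b) all abandonments of the target AVF within that window. These subjects stay in the denominator. Abandonments after the 6-month cut-off are not counted as 6-month failures, and in (a) abandonments for other reasons follow the 150-day rule. All abandonments will be listed by arm, study day and recorded reason.

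If the separate Statistical Analysis Plan already has such a rule, a cross-reference is enough. If there were no abandonments, one sentence in the report closes the point.

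**Cost.** One paragraph, one derived variable, two re-runs of an existing table and one listing. The reason is already required on the Exit Form; I assume the date is recorded too. The reason may need simple coding. No visit or consent change is needed, and the primary endpoint is not altered after enrollment closed in April 2022.

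**Downside.** Patency will be slightly lower in the sensitivity results. Version (a) relies on a reason given by an unblinded site. Version (b) avoids that judgement but also counts abandonments unrelated to patency. Both should therefore stand beside the primary result and not replace it.
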